9.7.1.2 Primary Analysis

The summaries of FH status, CV history and diabetic status and the summary statistics of LDL-C will be presented for the time of initiation of Repatha®.

9.7.2 Planned Method of Analysis

All summaries of the data will be descriptive in nature. For categorical variables the frequency and percentage, with 95% confidence interval, will be given.

Summary statistics for continuous variables will include the number of subjects, mean, median, standard deviation or standard error, 25th percentile (Q1), 75th percentile (Q3), minimum, and maximum.

For the outcome measure of LDL-C and other cholesterol values over time, the data collection period (up to 6 months pre-initiation of Repatha® and up to 30 months post-initiation of Repatha®) will be divided into time windows. For each subject the mean LDL-C and other cholesterol values during each time period will be obtained, and summary statistics will be produced based on these mean values. In order to optimally utilize the available LDL-C and other cholesterol data, the following time windows will be used:

Definition 1: Period of 6 months duration pre-initiation of Repatha® (to obtain baseline LDL-C), windows of 3 months duration post initiation of Repatha® (months 1-3, months 4-6, months 7-9 and so on, through months 28-30)

Definition 2: Period of 6 months duration pre-initiation of Repatha® (to obtain baseline LDL-C), windows of 6 months duration post initiation of Repatha® (months 1-6, months 7-12, months 13-18 and so on through months 25-30)

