9.3.2.1 Primary Outcome

Clinical characteristics at time of initiation of Repatha® as assessed in relation to:

- FH status (diagnosed/not diagnosed)
- CV history (see [Appendix B](#) for a list of diagnoses/events)

- Diabetic status (diabetic/not diabetic; Type 1 or Type II; HbA1C measurement closest to initiation of Repatha®)
- Cholesterol values including total cholesterol, LDL-C, HDL-C, non-HDL-C, triglycerides (value(s) available in the 26-week baseline period)
- Demographics (age at initiation of Repatha®, gender, country)
- Cardiovascular risk factors (body mass index (BMI), smoking status, chronic kidney disease, history of hypertension, vascular bed involvement (see also [Appendix B](#)))
- History of statin intolerance (y,n)
- Dose, dose frequency, commencement date of Repatha® administration
- Type, dose, dose frequency, commencement and discontinuation dates of other LMT administration including apheresis
- Dates and reason for hospital admittance/final diagnosis
- Dates of physician visits and reason for attendance

Of note, LMT use (including apheresis) over the 6 months prior to initiation of Repatha® will be summarised and the regimen in place at the time of Repatha® initiation will be regarded as the baseline.

In addition, LDL-C and other relevant lipid panel measurements and HbA1C as assessed within 6 months prior to initiation of Repatha® (or the mean of the two most recent LDL-C measurements, if there is more than one) will be regarded as the respective baseline values.

All CV history and diabetic status will be reported as baseline data

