9.5 Study Size

The primary outcome measures for the study involve estimating the percentage of subjects with clinical characteristics of interest (FH, CV history, diabetes - yes or no for each outcome measure) and also estimating the baseline LDL-C levels. The intention is to perform the analyses by country. The planned sample size for the study is 2000 subjects across approximately 15 countries; an average of approximately 130 subjects per country. The figure below shows the expected precision of estimates of the binary outcome measures for a range of sample sizes above and below 130 and for a range of percentages of subjects with and without the conditions of interest. This

gives an indication of the likely precision of estimates and demonstrates that the sample size per country will enable sufficiently precise estimates to be obtained for the primary outcome measures. For example, with a sample size of 130 in the country and assuming 35% of subjects have the condition being summarised, the ½ width of the 95% confidence interval around the estimate would be approximately 8%.

The table below shows the estimated precision of the continuous primary outcome measure, the mean LDL-C value prior to initiation of Repatha®, assuming a range of sample sizes and standard deviations (standard deviations based on those observed in phase 3 studies).

Standard deviation	½ width of 95% CI in mg/dL			
	N = 70	N = 100	N = 130	N = 150
40	9.37	7.84	6.88	6.40
45	10.54	8.82	7.74	7.20
50	11.71	9.80	8.60	8.00
55	12.89	10.78	9.46	8.80

The sample size will also enable the secondary outcome measures to be precisely estimated. This includes the LDL-C over time after initiation of Repatha, after allowing for missing data due to subject withdrawal (expected to be up to 10% per year over the 30 months follow-up period).

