9.9 Limitations of the Research Methods

9.9.1 Internal Validity of Study Design

9.9.1.1 Information Bias

For the primary objective, information bias is not anticipated to be applicable, as Investigators will be aware of the subjects' age and gender, and will have paid particular attention to their CV history as they have been referred for CV cause. It is possible that lipids may be measured more frequently in very high risk and/or sicker patients, which could influence the baseline LDL-C; to help prevent this, a maximum of two LDL-C values in the 6 months prior to initiation of Repatha® will be considered for inclusion in the baseline, and these will be the two most recent values prior to the initiation date.

For the secondary objectives, it is expected that Investigators will follow all subjects closely as: 1. they have been initiated on a novel therapeutic in the immediate post-launch period. LDL-C values and use of Repatha® and any concomitant medications will be significant markers of clinical care, and are likely to be assessed on an ongoing basis over the observation period. 2. Subjects are high risk patients in secondary care.

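### The pre-initiation window in section 9.7.2 carries no two-value cap, so the baseline point of the LDL-C-over-time summary can differ from the primary-outcome baseline

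*Protocol*

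**What the plan says.** Section 9.5 (Study Size) identifies "the continuous primary outcome measure, the mean LDL-C value prior to initiation of Repatha".

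Two sections define the baseline value with a cap:
- Section 9.3.2.1 (Primary Outcome) takes the measurement from the 6 months before initiation, "or the mean of the two most recent LDL-C measurements, if there is more than one) will be regarded as the respective baseline values".
- Section 9.9.1.1 (Information Bias) repeats this: "a maximum of two LDL-C values in the 6 months prior to initiation of Repatha® will be considered for inclusion in the baseline". Its reason is this: "It is possible that lipids may be measured more frequently in very high risk and/or sicker patients, which could influence the baseline LDL-C". It also settles which values count: "these will be the two most recent values prior to the initiation date".

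Section 9.7.2 (Planned Method of Analysis) describes the lipid-over-time summaries. It divides the whole data collection period, before and after initiation, into windows. It then states: "For each subject the mean LDL-C and other cholesterol values during each time period will be obtained". The summary statistics are built on those subject means. Definition 1 (3-month windows) and Definition 2 (6-month windows) open with the same entry: "Period of 6 months duration pre-initiation of Repatha® (to obtain baseline LDL-C". Neither definition has a cap or refers back to 9.3.2.1.

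**The concern.** Taken as written, 9.7.2 treats the 6 months before first dose like any other window: average the subject's values in it, and the result is baseline LDL-C. Sections 9.3.2.1 and 9.9.1.1 say that no more than two values may enter.

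A programmer following 9.7.2 would produce a baseline point for the over-time display that need not match the baseline in the primary table. It would also lack the protection that 9.9.1.1 offers against heavier testing in sicker patients, because those are the subjects likely to have three or more values. The protocol does not say which section takes precedence.

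**Working it through.** **1. The plan's own figure.** Inputs from 9.5: SD 40, 45, 50 and 55 mg/dL, N = 130 per country, 95% confidence. The half-width is 1.96 × SD / √N, with √130 = 11.402.

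| SD (mg/dL) | Computed | Stated in 9.5 |
|---|---|---|
| 40 | 6.876 | 6.88 |
| 45 | 7.736 | 7.74 |
| 50 | 8.595 | 8.60 |
| 55 | 9.455 | 9.46 |

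The other columns (N = 70, 100, 150) also reproduce to within 0.01. The table takes the SD as given, so it does not depend on which baseline rule is used.

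**2. When the two rules differ.** Let a subject have k values in the 6 months, and let d be the mean of the older values minus the mean of the last two. Then

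mean of all values − mean of last two = ((k − 2)/k) × d.

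- k = 1 or 2: the difference is 0, and the rules agree.
- k = 3: the difference is d/3.
- k = 4: the difference is d/2.

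With k ≥ 3 the rules still agree if d = 0. So they *can* differ with three or more values, but need not.

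**3. One subject (assumed values).** Oldest to newest: 190, 150, 140 mg/dL.
- Two most recent: (150 + 140)/2 = 145.
- All values: (190 + 150 + 140)/3 = 160.
- Difference: 15, which equals (190 − 145)/3.

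**4. Subject-level range.** The protocol gives no d, so d = 10, 20 and 40 mg/dL are assumed.
- k = 3: 3.3, 6.7 and 13.3 mg/dL.
- k = 4: 5, 10 and 20 mg/dL.

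**5. Country mean.** If a share q of subjects has k values and the rest have one or two, the shift is q × ((k − 2)/k) × d. The protocol gives no q, so 10% to 50% is assumed.
- k = 3, lowest: 0.10 × 10/3 = 0.33 mg/dL.
- k = 3, highest: 0.50 × 40/3 = 6.67 mg/dL.
- k = 4, for sensitivity: 0.10 × 10/2 = 0.5 to 0.50 × 40/2 = 10.0 mg/dL.

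**6. Sign.** The formula is linear in d. If older values are 10 to 40 mg/dL *lower* than the last two, the k = 3 range becomes −0.33 to −6.67 mg/dL.

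**The case against.** The strongest reply concerns scope. The window paragraph in 9.7.2 is introduced for lipids over time, which is a secondary outcome. The primary outcome has its own definition in 9.3.2.1, repeated with its rationale in 9.9.1.1. The primary-analysis text (9.7.1.2 and 9.7.2.4.1) summarises LDL-C at initiation and does not mention windows. On ordinary reading, the specific rule, stated twice, governs the primary outcome. This part stands. A reader might infer that the primary outcome itself has two incompatible definitions, but the documents do not support going that far.

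The reply also notes that 9.7.2 never says that all values are averaged. The 6-month entry could merely mark where eligible values are found, and averaging up to two of them would satisfy all three sections. That reading is possible but not the plain one. The paragraph calls for a mean over each window and counts the pre-initiation period among the windows. It also gives its aim as making the best use of the available lipid data, which points away from a cap. Even on the narrow scope, the over-time display would start from an uncapped value.

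Finally, 9.7.2.2 concedes that laboratory measurement may be infrequent, so few subjects may have three values in 6 months. This also stands: the effect could be negligible.

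**Conclusion.** The point holds as an inconsistency between 9.7.2 and the capped rule in 9.3.2.1 and 9.9.1.1. Its consequence is limited to the baseline point of the LDL-C-over-time summary. There, the value can disagree with the primary table for subjects with three or more pre-initiation values, and the stated bias control is lost.

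The size cannot be known from the protocol. Under the assumed ranges with three values per affected subject, a country mean moves by about 0.3 to 6.7 mg/dL. The planned half-widths at N = 130 are 6.88 to 9.46 mg/dL; more values per subject would enlarge the shift. No sample-size figure changes.

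Four stronger inferences are tempting but unsupported:
- *The uncapped mean inflates baseline and the apparent fall in LDL-C.* This needs older values to be higher. Section 9.9.2 also expects statin-intolerant patients; if a statin was stopped in the window, older values could be lower and the shift would reverse. In addition, 9.7.2 and 9.7.2.4.2 plan summaries by window, not a change from baseline.
- *The median-split subgroup is affected.* Section 9.7.2.5.1 says only baseline LDL-C and does not point to the window mean.
- *The other lipids default to an uncapped mean.* The two-value clause in 9.3.2.1 names LDL-C only, although its sentence covers the other lipids. That is unclear wording, but it sets no default.
- *Every subject with three or more values gets two different baselines.* Step 2 shows that the values can differ but need not.

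**What to change.** In Definitions 1 and 2 of section 9.7.2, state that the within-window mean applies to post-initiation windows only. State that the pre-initiation value is the 9.3.2.1 baseline: the single value, or the mean of the two most recent if there is more than one.

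Add that the same rule applies to the other lipids and wherever baseline LDL-C is used, including the median split. This removes the doubt over those uses without implying that they are now wrong.

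Separately, reconcile whether a value on the first-dose date counts as baseline. Section 9.2.5 includes that date in the baseline period, whereas 9.9.1.1 admits only values before the initiation date. Section 9.3.2.1 does not settle this, so it needs its own explicit statement.

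The cost is a few sentences of text. No new data are needed, and the precision table in 9.5 stands as it is.

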7.2 Rationale

EMA approval for Repatha® was granted on 17th July 2015. The data submitted in support of the filing were generated from an extensive interventional clinical trial programme in which selected populations were enrolled and managed according to strictly-defined protocols in a controlled setting. More recently, the 27,564 patient FOURIER trial which evaluated the effect of lowering LDL-C with evolocumab in subjects with established atherosclerotic disease reported a 20% relative risk reduction in major adverse cardiac events compared to those on optimized oral lipid lowering therapy ([Sabatine et al, 2017](#)). However, such data can not necessarily be generalised to routine clinical practice especially given the varying reimbursement rules and availability of the drug in participating countries, and at present there is little information describing Repatha® use in a real-world setting.

Across Europe, country health authorities grant local access approvals based on clinical trial data. As the next step, real world evidence describing product use in routine clinical practice are required, for continuation and/or reassessment of access. The design and objectives of this study address the anticipated requests being made by the health authorities. In particular, authorities require local real-world data on the patient population which is receiving Repatha®, including patient characteristics, dosing patterns and effectiveness in lowering LDL-C. The study will be conducted only in countries which require real world data to be collected in the post-launch setting and where it is allowed as per local regulations to study the use of a single treatment in clinical practice.

Data obtained from this study are intended to fulfil health authorities' requirements and to provide a robust source of published information for physicians.

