8.2 Secondary Objectives

- To describe LDL-C and other cholesterol concentrations over time
- To describe treatment patterns of use of Repatha® over time
- To describe treatment patterns of use of other lipid modifying therapies over time
- To describe Health Resource Utilisation components, including hospitalisations and physician visits

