9.2.6 Study Follow-up

Follow-up of each subject will be for 30 months after date of first administration of Repatha®, death, withdrawal of consent or loss to follow-up (whichever occurs earliest). Subjects will be followed regardless of continuation/discontinuation of Repatha®, including for subjects who received only one dose of Repatha®.

If subjects are lost to follow-up, the site will be encouraged to confirm the reason, which may include withdrawal of consent or relocation to a different physician.

Study duration is considered sufficient to allow an estimation of Repatha® and other LMT usage and LDL-C concentrations over time, following initiation of Repatha®.

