9.7.2.1 General Considerations

Statistical analyses will be descriptive only. No statistical inference or imputations of missing data are planned.

Subject demographics and baseline characteristics will be summarized. Summary statistics for continuous variables will include the number of subjects, mean, median, standard deviation or standard error, minimum, and maximum. For categorical variables, the frequency and percentage will be reported.

At the individual subject level, collection of data may be both retrospective and prospective, or prospective only. This depends on whether the subject enrolled some time after initiation of Repatha® (in which case their follow-up data is captured partially retrospectively) or whether the subject enrolled upon initiation of Repatha® (in which case the subject's follow-up data is collected prospectively in its entirety). Data obtained from subjects whose follow-up data are in part collected retrospectively may be reported separately from those with data collected fully prospectively to assess the potential for systematic differences between these subject groups.

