9.7.2.2 Missing or Incomplete Data and Lost to Follow-up

The primary outcome measures are commonly recorded and/or already known to the treating physician. Incomplete information is not expected in this regard.

To evaluate the secondary objectives, the study intends to capture variables expected to be recorded as part of routine follow-up in this cardiovascular high risk population.

Measurement of laboratory variables (eg LDL-C) may be infrequent, however Investigators are expected to be interested in checking this parameter more closely following administration of a novel therapeutic, hence it is expected that LDL-C measurements will be taken during the follow-up period of all subjects enrolled in the study. Likewise, accuracy in reporting use of Repatha® and concomitant LMTs can be expected in this situation.

Where data appears to be incomplete in the study database, the study monitor will encourage sites to provide as much information as possible, from patient notes.

For relevant calendar dates that are partially complete, where possible an algorithm will be utilised to impute eg the missing day. Details of this algorithm are described in the statistical analysis plan. There will be no imputation for any other missing data fields.

Based upon data from the long-term Phase III studies Descartes and Osler ([Blom et al 2014](#), [Sabatine et al 2015](#)), a lost-to-follow-up rate of around 10% might be expected in this study. However, the low dropout rate in long-term interventional Phase III studies of evolocumab indicates subjects' willingness to continue on therapy. The incidence of discontinuation may be expected to be lower in an observational study, which does not carry the burden of additional study visits and invasive laboratory investigations.

Subjects lost to follow up will not be replaced.

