9.7.2.4.2 Analysis of Secondary Endpoints

Summaries displaying frequency and percentage, with 95% confidence intervals will be presented for gender, country, use of Repatha® (at initiation of Repatha® and over time), lipid-modifying therapies (at initiation of Repatha® and over time), medication adherence, medication persistence, incidence of hospitalization (including reason for admittance/final diagnosis), and incidence of physician visits.

Summary statistics displaying the number of subjects, mean, median, standard deviation or standard error, 25th percentile (Q1), 75th percentile (Q3), minimum, and maximum will be presented for age (at initiation of Repatha®) and LDL-C over time.

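### LDL-C over time is planned as window means over whoever was tested, on or off Repatha, with no within-subject change, so the tables may not isolate how far LDL-C was lowered

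*Protocol*

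**What the plan says.** Section 9.7.2 fixes the method. Time is cut into a 6-month pre-initiation period and 3-month or 6-month windows after initiation, and then: "For each subject the mean LDL-C and other cholesterol values during each time period will be obtained, and summary statistics will be produced" based on those means. Section 9.7.2.4.2 adds only that summary statistics "will be presented for age (at initiation of Repatha®) and LDL-C over time". The matching objective in section 8.2 is "To describe LDL-C and other cholesterol concentrations over time".

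Three other statements determine which values enter a window:

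- Section 9.2.6: "Subjects will be followed regardless of continuation/discontinuation of Repatha®, including for subjects who received only one dose of Repatha".
- Section 9.7.2.1: "No statistical inference or imputations of missing data are planned". Section 9.7.2.2 makes an exception for partial dates only.
- Section 9.7.2.2: "Measurement of laboratory variables (eg LDL-C) may be infrequent". It expects LDL-C to be measured at some time in follow-up for every subject, but does not say in every window.

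Section 7.2, like the abstract, says that authorities need local real-world data, "including patient characteristics, dosing patterns and effectiveness in lowering LDL-C".

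**The concern.** Lowering is a change within a patient. The planned tables give a baseline mean and a series of window means, each over the subjects who happen to have a value. A reader who wants the reduction has to subtract one mean from another, and the two may come from different subsets of the cohort. A subject who stops mid-window contributes one figure that blends both states, and the published summary cannot undo that.

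If the curve rises over 30 months, the cause could be patients stopping, a shift in who is tested, or a real loss of effect. These have different meanings for an authority reassessing access. The protocol recognises the relevant biases in section 9.9.1, but its remedies stop at the baseline or primary outcome.

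**Working it through.** **1. The plan's own precision figures.** Section 9.5 gives half-widths for mean LDL-C before initiation. With 1.96 × SD/√N, SD 50 and N = 130: 1.96 × 50/√130 = 8.60 mg/dL, as stated. The other entries agree to within 0.01. The binary example, 1.96 × √(0.35 × 0.65/130) = 8.2%, agrees with the stated 8%. With withdrawal of 10% per year (section 9.5), 130 subjects become 130 × 0.9^2.5 = 99.9 at 30 months, or 130 × 0.75 = 97.5 if the loss is linear. The half-width at SD 50 is then 9.8 to 9.9 mg/dL. These figures are sound, but they concern sampling error only.

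**2. Do the safeguards reach LDL-C over time?**

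- Section 9.9.1.1 accepts that sicker patients may be tested more often. Its remedy, a maximum of two values, applies to baseline.
- Section 9.9.1.2 accepts that dropout may depend on LDL-C. Its completer analysis is for the primary outcome, which is measured at initiation.
- Section 9.7.2.5 subsets by amount of retrospective capture.
- Section 9.7.2.5.1 defines subgroups by country and by status at initiation.

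None of these splits by Repatha status at sampling or by whether a subject was tested.

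**3. Effect of values taken after stopping (illustration).** Let f be the share of measured subjects who are off drug, and assume that their LDL-C is fully back at baseline. The mean reduction is then (1 - f) × the on-drug reduction. For f = 5%, 10%, 20% and 30%, that is 95%, 90%, 80% and 70% of it. The protocol gives neither f nor the degree of return.

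**4. Effect of selective testing (illustration).** If on-drug and off-drug subjects are tested with probabilities a and b, the off-drug share among those tested is f·b/[(1 - f)·a + f·b].

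| f | a, b | Off-drug share among tested | Mean reduction as share of on-drug reduction |
|---|---|---|---|
| 10% | equal | 10% | 90% |
| 10% | 0.4, 0.8 | 0.08/0.44 = 18% | 82% |
| 10% | 0.8, 0.4 | 0.04/0.76 = 5% | 95% |
| 20% | equal | 20% | 80% |
| 20% | 0.4, 0.8 | 0.16/0.48 = 33% | 67% |
| 20% | 0.8, 0.4 | 0.08/0.72 = 11% | 89% |

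The shift can go either way. More generally, if a share q is tested and tested and untested subjects differ by k standard deviations, the window mean moves by (1 - q) × k × SD. At SD 50 that is 0.5 mg/dL (q = 0.9, k = 0.1), 3.75 (q = 0.7, k = 0.25) or 12.5 (q = 0.5, k = 0.5). All values of a, b, q and k are assumed.

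**5. What pairing offers.** With N = 130 and SD 50 at both times, two means treated as independent give a half-width for their difference of 1.96 × 50 × √(2/130) = 12.16 mg/dL. Paired change gives 1.96 × 50 × √(2(1 - ρ)/130), which is 10.17, 8.60 and 6.66 for assumed correlations of 0.3, 0.5 and 0.7. Pairing also compares each subject with the same subject.

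**6. Which baseline?** Sections 9.3.2.1 and 9.9.1.1 use the two most recent LDL-C values before initiation. Section 9.7.2, read literally, averages every value in the 6-month pre-initiation period. For a subject with three or more values the two can differ, so change from baseline is not yet uniquely defined.

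**The case against.** The strongest reply is that the plan does what its objective asks. Section 8.2 asks for concentrations over time in people who started Repatha, and following them after they stop is deliberate. For that quantity, post-stopping values belong in the mean. Real-world effectiveness can itself include discontinuers, and section 7.2 defines no on-drug effect. This stands: the all-initiator display should remain the main summary.

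A reader might go further and infer that the planned LDL-C result is diluted and confounded. The documents do not support that. Dilution is relative to an on-treatment quantity that the protocol never adopts. Selective observation is a risk whose size and sign cannot be derived from the text, and it is not confounding. Section 9.7.2.2 cites about 10% loss to follow-up in the phase 3 studies and suggests that discontinuation may be lower here, so large off-drug shares have no support. Subjects who withdraw from the study add no off-drug values at all.

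Nor are the tables blind to discontinuation. Repatha use and persistence are summarised (section 9.7.2.4.2), and each summary gives the number of subjects. That helps, but only in part: persistence among all initiators is not the off-drug share among those tested in a window, and n does not show who is missing.

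Finally, change from baseline may be in the statistical analysis plan, which is not shown. Its absence from the protocol alone would be no finding. The averaging of all values within a window over whoever was tested is, however, fixed in the protocol itself, and a paired display improves on that stated method.

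**Conclusion.** The point holds in limited form. The stated method is a valid description of all initiators. It is weak support for the lowering effect that the rationale cites, because it pools values within a window regardless of treatment status, lets the set of subjects vary and names no within-subject change. The safeguards against selective testing and differential dropout do not reach this outcome.

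No bias is demonstrated. The (1 - f) factor assumes full return to baseline after stopping, and the testing illustrations rest on assumed rates. The 8.60 mg/dL half-width refers to baseline LDL-C and serves only as a sense of scale. The change is worth making because the data needed are already collected.

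**What to change.** Keep the all-initiator window display as the main summary. Then:

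1. Reconcile sections 9.3.2.1, 9.9.1.1 and 9.7.2 so that one baseline LDL-C definition applies throughout.
2. Add to section 9.7.2.4.2 the absolute and percentage change from the subject's own baseline, among subjects with both values, with N and 95% CI per window.
3. Add a supplementary version that uses only values taken while on Repatha. Label it as conditional on persistence, since those who stay on treatment may be the better responders. State in advance how missed doses, gaps and samples taken soon after stopping are classified for this analysis.
4. Report baseline LDL-C for subjects with and without a value in each window.

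No new data are needed: Repatha start and stop dates, missed doses and cholesterol assessments are already in the schedule (Appendix C). The cost is more tables, across 10 three-month and 5 six-month windows in about 15 countries. Off-drug groups would be small: if 10% of 130 are off drug, that is 13 subjects, with a half-width of 1.96 × 50/√13 = 27 mg/dL at SD 50. Any on/off split is therefore best shown pooled, or only in countries where numbers allow.
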